4.3 Modified Follow-Up & Off Study Criteria

4.3.1 Criteria for Modified Follow-Up

The following criteria will result in the patient being ineligible for further treatment on the protocol, although response data will continue to be collected as applicable:

- 4.3.1.1 Any patient who develops irreversible, life threatening, Grade 3-4 acute GvHD within 42 days, Grades 3-5 non-hematologic adverse event within 28 days from last VST dose and considered to be primarily related to VST injection. In such patients, the toxicities will be followed until resolution or until their off study date.
- 4.3.1.2 Any patient who receives any other hematopoietic cell product. In such patients, adverse event data collection will cease.
- 4.3.1.3 Any patient who receives therapy for relapse of their primary malignancy. In such patients adverse event data collection will cease.
- 4.3.1.4 Any patient who experiences Grade 3 or 4 cytokine release syndrome that persists beyond 72 hours. In such patients, the toxicity will be followed until resolution or until their off study date.

Patients who meet “modified follow-up” criteria remain on long-term follow-up as per the required assessments table 4.2.2.

4.3.2 Off Study Criteria

- 4.3.2.1 Completion of study specified procedures.
- 4.3.2.2 Refusal of further study follow-up by patient or legal guardian
- 4.3.2.3 Lost to follow up
- 4.3.2.4 Death

5 STATISTICAL CONSIDERATIONS

5.1 Study Design Synopsis

This study is designed as a single-arm pilot study to evaluate the feasibility, safety and efficacy of most closely HLA matched multivirus specific VST lines (CHM-VSTs) in HSCT patients with either of five viruses; BK virus, HHV6, EBV, CMV and adenovirus persistent despite of standard therapy. The study first conducts a phase IIA trial to evaluate the clinical response rate. After the phase IIA trial, if the data suggests excellent clinical responses that warrant further investigation, the study will be expanded to recruit 30 additional patients to evaluate the role of HLA matching on viral outcomes.

The total sample size of the study will be a maximum of 80 patients who receive at least one VST infusion. The sample size for the phase II A trial is 50 patients who receive at least one VST infusion. A larger number of potential subjects will be screened to assess the feasibility of the approach.

CHARMS Protocol v1.0 (10.30.13)	Version 5.0 (10.6.15)
Version 2.0 (12.09.13)	Version 6.0 (08.29.16)
Version 2.1 (03.07.14)	Version 7.0 (04.26.17)
Version 3.0 (06.17.14)	Version 8.0 (05.24.17)
Version 4.0 (11.06.14)	Version 9.0 (08.10.17)

We expect to enroll 15-20 patients per year and therefore expect the study to conclude within the estimated accrual period of 4 years.

5.2 Sample Size Determination and Design Characteristics

Frist, the study will conduct a single arm pilot study using a phase IIa design. Simon's two-stage Minimax design⁶⁰ will be used to for the single-arm pilot study. Under the null hypothesis that the VST is not active, the data from previous trials suggest that the true response rate is 20% in anti-viral activity, where a positive response is defined as the viral load reduction to the normal level for at least one of the 5 virus types (CMV, EBV, adenovirus, BK virus and HHV6) within 42 days following the initial treatment of VST.

Allowing a 5% type-I error and 90% power, the null hypothesis will be tested against a one-sided alternative that the true response rate is 40%. The maximum size is 45 eligible patients, defined as the patients who receive the VST infusion and who can finish the 42 days follow-up. We anticipate that most patients will finish the follow up and will allow a 10% drop out rate. Therefore, the maximum sample size is 50.

The phase IIa trial operates in two stages, where the first stage recruits 24 patients. The trial pauses at the end of the first stage to make the decision on whether to stop the trial early due to lack of enough efficacy for treating viral infection, according to the rule as follows. Of the 24 patients at the first stage, if 5 or fewer positive responses are observed, then the study will be stopped. Otherwise, 21 additional patients will be accrued to reach the goal of 45 accruals. At the end of the trial, the null hypothesis will be rejected, if 14 or more positive responses are observed in among the 45 patients. This design has 65.6% chance to stop early when the true response rate is 20%.

After the phase IIa trial suggests excellent clinical responses that warrant further investigation, the study will be expanded to recruit 30 additional patients to evaluate the viral reduction based HLA matching. We hypothesize the viral reduction among the low HLA matching group (1/8, 2/8, or 3/8 HLA matching) is not worse than the high HLA matching group (4/8, 5/8, 6/8, 7/8, or 8/8).

The sample size is calculated based on non-inferiority trial for comparing two-sample means. Based on the preliminary data, the standard deviation of viral reduction is about 18. We assume that the viral reduction in the low HLA matching group is not inferior to the high HLA matching group when the difference in the viral reduction between the two groups is no less than -10 (non-inferiority margin). Preliminary data suggest that the ratio of sample size between the low and high HLA matching groups is 5 to 7. A sample size of 30 patients with low HLA matching and 42 with high HLA match (total 72) would have at least 85% power to test the non-inferiority hypothesis with 2-side 5% alpha level. Assuming 10% of patients to be lost to follow-up, then the study will recruit up to a total of 80 patients.

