- ii. JC virus disease is defined as defined as the presence of JC virus detectable by culture or PCR in one or more sites such as blood or CSF and symptoms of disease including symptoms of PML OR detectable JC virus by PCR or culture in more than one site.

3. Patients with multiple CMV, EBV, Adenovirus, HHV6 and BK virus infections are eligible given that each infection is persistent despite standard therapy as defined above. Patients with multiple infections with one or more reactivation and one or more controlled infection are eligible to enroll.
4. Clinical status at enrollment to allow tapering of steroids to equal or less than 0.5 mg/kg/day prednisone (or equivalent).
5. HgB>8.0

CHARMS Protocol v1.0 (10.30.13)	Version 5.0 (10.6.15)
Version 2.0 (12.09.13)	Version 6.0 (08.29.16)
Version 2.1 (03.07.14)	Version 7.0 (04.26.17)
Version 3.0 (06.17.14)	Version 8.0 (05.24.17)
Version 4.0 (11.06.14)	Version 9.0 (08.10.17)

6. Pulse oximetry of > 90% on room air
7. Available multivirus-specific VSTs
8. Negative pregnancy test in female patients if applicable (childbearing potential who have received a reduced intensity conditioning regimen).
9. Written informed consent and/or signed assent line from patient, parent or guardian.

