3.1.2 Antiviral Activity

Peripheral blood and, where relevant, stool and urine will be monitored for CMV, EBV, adenovirus, BK virus, JC virus and/or HHV6 viral load. For the infection under treatment response in viral load will be defined as follows:

Complete response: Return to normal range as defined by specific assay used and clinical signs and symptoms.

Partial response: Decrease in viral load of at least 50% from baseline or 50% improvement of clinical signs and symptoms

Mixed response: Decrease in viral load of at least 50% from baseline for one infection and an increase or no change in viral load for a second infection (only applicable for patients with two or more infections at baseline).

Stable disease: Changes insufficient to qualify as partial response or progression

Progression: Increase in viral load of at least 50% from baseline or dissemination to other sites of disease.

Viral response data will be reviewed by a consensus committee of investigators.

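### The Simon responder rule in Section 5.2 is not tied to the infection under treatment and gives no rule for patients with several treated infections; the stated 5% error holds only if 20% is the patient-level rate for that rule.

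*Combined protocol and SAP*

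**What the plan says.** All references are to the combined protocol and SAP.

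- **Section 5.2 (sample size).** The null is that "the true response rate is 20% in anti-viral activity". In the same sentence, a responder is someone whose load falls to normal "for at least one of the 5 virus types". The five named there are HHV6, BK virus, adenovirus, EBV and CMV, and the window is 42 days from the initial treatment. The design sets its errors by "Allowing a 5% type-I error and 90% power", with the null "tested against a one-sided alternative that the true response rate is 40" percent. In operation, "the first stage recruits 24 patients"; the study stops at 5 or fewer responders, and otherwise continues to 45 and rejects the null at 14 or more.
- **Section 3.1.2 (antiviral activity).** The endpoint definitions open with "For the infection under treatment response in viral load will be defined as follows". A separate mixed category covers a patient in whom one infection falls by at least half while a second rises or does not change.
- **Section 2.3.1 (inclusion).** "Patients with multiple infections with one or more reactivation and one or more controlled infection are eligible to enroll". Patients also qualify after treatment failure, through intolerance of standard therapy, or with JC virus.
- **Section 4.2.2.** The text schedules post-infusion loads for the treated virus or viruses and follows others if the treating team measures them. Table 4.2.2 lists the five viruses where previously positive.

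**The concern.** Sections 5.2 and 3.1.2 judge response on different infections. Section 3.1.2 looks at what is being treated. Section 5.2 looks at any of five viruses and is silent on whether that virus was the reason for the infusion.

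Two kinds of patient expose the gap:

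1. A patient treated for one virus who also carries a second, controlled virus that is still above the normal range. If the second normalises and the treated one progresses, 5.2 counts a responder.
2. A patient treated for two viruses. If one normalises and the other progresses, 5.2 counts a responder, whereas 3.1.2 has a mixed category for this picture.

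JC virus shows the same detachment: it is an eligible treated infection but not among the five, so a patient treated only for JC virus could respond only on some other virus.

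The same count feeds the futility stop and the final test, and it informs the decision to add 30 patients. What is at stake is what a positive result would mean and, depending on what the 20% represents, whether the stated error rate applies.

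**Working it through.** **Inputs from Section 5.2.** Null 20%, alternative 40%, first stage 24 with stop at 5 or fewer, total 45 with rejection at 14 or more.

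**Step 1: reproduce the plan.** With response probability *p* per patient:

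- early stop = P(X₁ ≤ 5), X₁ ~ Bin(24, *p*)
- reject = Σ over x ≥ 6 of P(X₁ = x) × P(X₂ ≥ 14 − x), X₂ ~ Bin(21, *p*)

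| *p* | Early stop | Reject |
|---|---|---|
| 0.20 | 65.6% | 4.83% |
| 0.40 | 4.0% | 90.0% |

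The early-stop figure matches the stated 65.6%. Type I error is within 5% and power is 90%. An exhaustive search returns the same minimax design, and 45 / 0.9 = 50. The arithmetic is correct, provided that 20% is the null probability that a *patient* meets the rule actually applied.

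**Step 2: which viruses can count.** The rule needs a reduction to the normal level. A virus already normal at baseline cannot meet it. One that is above normal but not under treatment can, and so can any one of several treated viruses. Table 4.2.2 means data on a previously positive virus can be on file.

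**Step 3: what if 20% is a per-infection rate?** This is an assumption; the plan does not say so. The share *m* of patients with two viruses is not given either, so 10% and 25% are used for illustration.

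*Two independent viruses.* The chance that at least one normalises is 1 − 0.80² = 0.36, so *p* = (1 − *m*) × 0.20 + *m* × 0.36.

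- *m* = 10%: 0.180 + 0.036 = 0.216
- *m* = 25%: 0.150 + 0.090 = 0.240

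*Positively correlated viruses.* Take an any-virus rate of 0.28, halfway between 0.20 (the two always agree) and 0.36 (independent).

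- *m* = 10%: 0.180 + 0.028 = 0.208
- *m* = 25%: 0.150 + 0.070 = 0.220

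| Two-virus share | Dependence | *p* | Early stop | Type I error |
|---|---|---|---|---|
| 10% | independent | 0.216 | 58.0% | 8.3% |
| 25% | independent | 0.240 | 46.7% | 16.1% |
| 10% | correlated | 0.208 | 61.8% | 6.4% |
| 25% | correlated | 0.220 | 56.1% | 9.4% |

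**Step 4: a lower per-infection rate.** Section 1.10 gives a 13% response in 8 patients without a line who continued standard therapy. If 13% were the per-infection rate, two independent viruses give 1 − 0.87² = 0.243. Then:

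- *m* = 10%: 0.90 × 0.13 + 0.10 × 0.243 = 0.141, type I error 0.3%
- *m* = 25%: 0.75 × 0.13 + 0.25 × 0.243 = 0.158, type I error 0.7%

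So the direction, not just the size, of any departure from 5% depends on what the 20% stands for.

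**The case against.** The strongest defence is that 5.2 attaches the 20% to the patient-level any-of-five definition in one sentence. Read literally, the error is 4.83% and nothing is inflated. The documents show no source for the 20%, but that leaves it unverified; it does not make it a per-virus rate. The 13% figure, from only 8 patients, would even leave room for a multi-virus mix. This stands, and it makes every figure in Step 3 conditional.

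A reader might also infer that a patient with a controlled second virus is credited automatically. The documents do not support that. A virus normal at baseline is excluded by the reduction requirement, and a controlled virus that is still abnormal is not certain to normalise. The term controlled is undefined, and the frequency of such patients is not given.

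Further points have some weight. Section 3.1.2 sends response data to a consensus committee of investigators. Section 5.4 tabulates complete, partial and mixed responses. The text of 4.2.2 schedules loads for treated viruses only. The prior third-party study lists each of its 50 patients under one virus (23 + 18 + 9). Antiviral response is a secondary endpoint, and the expansion depends on excellent clinical responses, not expressly on 14 of 45 alone. These narrow the consequence. None of them supplies the missing rule: 5.2 does not refer to 3.1.2, and a patient treated for two viruses can still qualify on either.

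**Conclusion.** The mismatch between 5.2 and 3.1.2 is definite and rests on wording alone. As written, a patient can be a responder in the futility and final counts on an untreated virus that was above normal, or on one of several treated viruses, while another treated infection progresses.

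Its statistical size is conditional. If 20% is the true patient-level rate for the rule used, the stated 5% holds. If 20% is a per-infection rate, type I error would be about 6% to 16% for two-virus shares of 10% to 25%, depending on correlation. Neither the share nor the correlation is in the documents, so it would go too far to say that the trial's error rate is inflated. The point should be corrected because the go/no-go count must have one clear meaning and the null must refer to it.

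**What to change.** In Section 5.2:

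1. Replace the any-of-five phrase by: *reduction to the normal level of the infection(s) for which the VSTs were given (any qualifying route in 2.3.1) that were above the normal range at baseline*. Naming all routes keeps infections enrolled because standard therapy was not tolerated. The text should also make clear how patients treated for JC virus count.
2. State one patient-level rule for patients with several treated infections (for example any, all, or a pre-named index infection). Step 1 alone leaves this open.
3. Confirm that the 20% null refers to that rule, and give its basis.
4. Add a pre-specified sensitivity count in which a patient responds only if all treated infections normalise, and a table of response by number of treated viruses.

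If 20% is confirmed for the chosen rule, the 24/45 design and its boundaries stay as they are. The cost is revised wording and one extra table. The downside is that the reported response rate may be slightly lower.

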received an intravenous infusion of up to 2×10^7 VSTs/m² and were eligible for additional infusions at intervals of at least 2 weeks, in the event of a partial response (PR). Of the 50 patients who received VST infusions 23 received VSTs for persistent CMV, 18 for persistent adenovirus, and 9 for refractory EBV-PTLD. Five of the 50 treated patients withdrew from the study or died of their underlying disease.

From the bank of 32 VST lines a suitable line was identified for 90% of the screened patients within 24 hours. Of the 50 patients who were treated with these VSTs 74.0% had a CR or PR (73.9% for CMV, 77.8% for AdV, and 66.7% for EBV), including responses in 6 of 9 patients with refractory EBV-PTLD, and most of these responses (89%) were durable. By contrast 8 patients in the study for whom a line was not available and who continued with “standard therapy” demonstrated a 13% response rate, and 6 (75%) died of viral disease.

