5.4 Data Analysis

Safety and toxicity outcomes including adverse events, GvHD, clinical signs of viral infections, secondary graft failure and laboratory measurements will be summarized using descriptive statistics (frequency table, means, standard deviations, medians and ranges). Toxicity information including the type, severity, time of onset, time of resolution, and the probable association with the study regimen will be tabulated and summarized.

Response rate including complete response, partial response and mixed response will be summarized as frequency table. The response rate with 95% CI will be reported. Reconstitution of antiviral immunity using multimer analysis and ELISpot assays will also be summarized using descriptive statistics at each time point. Pairwise comparisons will be performed to compare changes of these immunological parameters from VST infusion to each time point of post-infusion measurements using paired t-tests or Wilcoxon signed-ranks tests. The normality assumption will

CHARMS Protocol v1.0 (10.30.13)	Version 5.0 (10.6.15)
Version 2.0 (12.09.13)	Version 6.0 (08.29.16)
Version 2.1 (03.07.14)	Version 7.0 (04.26.17)
Version 3.0 (06.17.14)	Version 8.0 (05.24.17)
Version 4.0 (11.06.14)	Version 9.0 (08.10.17)

be assessed and transformations to achieve approximate normality will be carried out if necessary. Overall survival post VST infusion will be analyzed by the Kaplan-Meier method.

Viral load reduction will be compared between the low and high HLA using the two-sample t-test. Additionally, Viral load levels will be correlated with immunological parameters using correlation coefficients. Longitudinal analysis is employed to model repeatedly-measured immunologic parameters. This will allow us to model patterns of immune response per patient while allowing for varying intercepts and slopes for a patient. Viral load levels will be correlated with immunological parameters using correlation coefficients. These modeling strategies will be considered exploratory in nature due to the limited patient numbers in this initial trial.

Overall survival since allogeneic hematopoietic stem cell transplant will be analyzed using the Kaplan-Meier method. Cumulative incidences to the time of complete/partial resolution of viral infection and viral load reduction, considering death a competing event, will be analyzed in univariate and multivariate model using the Fine and Gray method.

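### The HLA-match non-inferiority comparison has no unit or time point for viral reduction, its inputs give about 64% power rather than at least 85%, and on a percent scale one patient can make it fail

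*Combined protocol and SAP*

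**What the plan says.** After phase IIa, section 5.2 of the combined protocol and SAP adds 30 patients to ask whether lines with low HLA match (1/8 to 3/8) reduce virus no less than lines with high match (4/8 to 8/8). The basis is given as: "The sample size is calculated based on non-inferiority trial for comparing two-sample means". The inputs are:

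- Spread: "the standard deviation of viral reduction is about 18", attributed to preliminary data. These preliminary data are not shown.
- Margin: low match is non-inferior when "the difference in the viral reduction between the two groups is no less than -10 (non-inferiority margin".
- Group sizes: "the ratio of sample size between the low and high HLA matching groups is 5 to 7", giving 30 low and 42 high, 72 in all, raised to 80 for 10% loss.
- Stated result: power of at least 85% at a two-sided 5% level.

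The analysis in section 5.4 is one sentence: "Viral load reduction will be compared between the low and high HLA using the two-sample t-test".

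Neither section gives the unit of viral reduction, the day of measurement, the score for a rising load, the value for an undetectable result, or the value used when a patient has several treated viruses. Section 3.1.2 defines response and progression by percent change from baseline.

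**The concern.** The SD, the margin and the test all sit on a scale that is never named, so two analysts could compute different endpoints from the same data and reach different conclusions.

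Two consequences follow. The power statement can be checked without knowing the unit, because it depends only on the ratio of margin to SD, and it does not reproduce. And if the unit is percent, the t-test acts on a quantity that is capped on one side only. Patients enrol with infections that have persisted despite therapy, so some rising loads are foreseeable, and section 3.1.2 sets no upper limit on progression.

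This comparison is the reason given in section 5.1 for the 30-patient expansion. At stake is whether the trial can answer that question, and whether its answer reflects match level or a single viral load.

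**Working it through.** **1. The plan's own power figure.** Inputs from section 5.2: SD 18, margin 10, groups of 30 and 42, two-sided 5% (one-sided 2.5% for non-inferiority). The true difference is not stated; I take 0.

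- SE = 18 × √(1/30 + 1/42) = 18 × 0.2390 = 4.30
- Power = Φ(10/4.30 − 1.96) = Φ(0.364) = 64.2% (63.0% with the noncentral t)

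Variants tried:

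| Variant | Power |
|---|---|
| One-sided 5% | 75.1% |
| All 80 patients (33 and 47), stated alpha | 68.7% |
| Equal groups of 36, stated alpha | 65.4% |
| One-sided 10% | 85.1% |

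Only a one-sided 10% level reproduces the plan: it needs exactly 72 patients. That is not the stated alpha. The allowance for loss is correct (72/0.9 = 80).

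**2. What 85% would need at the stated alpha.** With a 5:7 ratio, 1/n(low) + 1/n(high) = 2.4/n(high).

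- n(high) = 2.4 × 18² × (1.960 + 1.036)² / 10² = 69.8, so 70 high and 50 low, 120 evaluable in total.
- Keeping 30 and 42: SD = 10 / (2.996 × 0.2390) = 14.0.
- Keeping SD 18 and 30 and 42: low match would have to be truly better by about 2.9, which the plan does not assume.

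**3. Which unit.** The largest change quoted is a 6 log fall (section 1.8.5.2). An SD of 18 and a margin of 10 cannot be log10 units against that. Percent change, the scale of section 3.1.2, is the working reading.

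**4. One patient on the percent scale.** A tenfold rise scores 100 × (1 − 10) = −900. Replacing a patient at +75, it shifts the mean by 975/30 = 32.5 points in the low group or 975/42 = 23.2 in the high group, against a margin of 10.

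Constructed example: both groups with mean 80 and SD 10, one value replaced, lower 95% limit for low minus high (pass if above −10).

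| Replaced value | Pooled | Welch |
|---|---|---|
| None | −4.8 | not run |
| One low-match patient at −50 | −13.0 | −14.4 |
| One low-match patient at −900 | −87.8 | −99.6 |
| One high-match patient at −50 | −5.6 | −4.7 |
| One high-match patient at −900 | −32.1 | −24.0 |

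A modest rise in one low-match patient is enough to fail. In the high group it takes a large one. To look for a false pass, I set low match truly 15 points worse (70 against 85, SD 10). The limit is −19.8; with one high-match patient at −900 the observed difference turns to +8.4, but the limit falls to −47.2. The outlier inflates the SD, so the result still fails.

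**5. Is 18 a plausible SD for percent change?** This step is illustrative. Section 1.10 reports of an earlier study: "Of the 50 patients who were treated with these VSTs 74.0% had a CR or PR". With 74% responders, the spread between the two classes alone is √(0.74 × 0.26) = 0.439 times the gap in their means. SD 18 therefore allows a gap of at most 18/0.439 = 41 points: non-responders must average at least a 34% fall if responders average 75%, or 49% if responders average 90%. No document gives these means. For assumed pairs:

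| Responders / others (assumed mean fall) | Between-class SD | Power, 30 and 42 |
|---|---|---|
| 75% / 25% | 21.9 | 48% |
| 90% / 25% | 28.5 | 31% |
| 90% / 0% | 39.5 | 18% |

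The donor-derived results in section 1.8.5.2 (11 treated infections: 8 complete responses, 2 partial, 1 none) give a minimum SD of about 14, or about 28 if the non-responder did not change. SD 18 is attainable there.

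**The case against.** A reader might infer from step 5 that SD 18 contradicts the protocol's own response data, and that true power lies between 18% and 48%. The documents do not support that. The 74% comes from an earlier three-virus product made by a different process, it does not separate complete from partial responses, and under section 3.1.2 a partial response can be reached on clinical signs alone. The data behind the 18 are not shown, the assumed means are mine, and the donor-derived results can accommodate 18. What stands is that 18 looks low if about 74% respond and non-responders fall little, so its source should be given.

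A reader might also infer that an outlier could produce a false claim of non-inferiority. None of the computed examples did so. The harm seen is lost power.

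The tenfold rise is hypothetical: no document reports one in a treated patient, and the plan might floor rises at some value. It does not say so, however, and one low-match patient at −50 already suffices in the example. Some fragility would remain on any scale: at SD 18 the 95% half-width is about 8.6, so an observed difference below about −1.4 fails.

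Section 5.4 does mention normality checks and transformation, but in the passage on paired tests of immunological parameters, not with the HLA comparison. A transformation there would leave a margin of 10 and an SD of 18 without meaning. The planned Fine and Gray analysis of viral load reduction is a separate analysis and does not define this endpoint.

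**Conclusion.** The concern holds on three points. The endpoint of the HLA comparison has no unit or time point. On the stated inputs its power is about 64%, not at least 85%; this rests on a true difference of 0 and on no choice of unit. On percent change, the only workable reading, a plain t-test can be made to fail by one patient: about 32 points of shift in a 30-patient mean for a tenfold rise, against a margin of 10.

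The low-looking SD is a reason to ask for its source, not a demonstrated error. This should be corrected before the comparison is analysed. It does not touch the phase IIa response test or the safety monitoring.

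**What to change.** In sections 5.2 and 5.4:

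1. Define viral reduction as log10(baseline) minus log10(day 42), stating which infusion day 42 counts from. Set undetectable results to the assay limit. State one rule for patients with several treated viruses, and how deaths before day 42 are handled.
2. Compare the groups with adjustment for baseline log10 load, and for virus where numbers allow. On this scale a tenfold rise scores −1; replacing a 75% fall (+0.60), it moves a 30-patient mean by 1.60/30 = 0.05 log10.
3. Re-express the SD and the margin in log10 units from the phase IIa data, and give their source. Those patients also enter the comparison (50 + 30 = 80), so use the SD pooled over match groups and fix the margin without looking at results by match.
4. Restate the power that 30 and 42 patients give, with the assumed true difference. On the current inputs it is about 64%.

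The cost is SAP wording and a lower stated power. Baseline and day 42 viral loads are already in the assessment schedule, so no extra patients or samples are needed. Keeping the 85% claim on the current inputs would take about 120 evaluable patients.

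### The HLA-matching non-inferiority comparison is said to have at least 85% power, but the plan's inputs (30 vs 42, SD 18, margin 10, two-sided 5%) give about 63% if the groups are truly equal

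*Combined protocol and SAP*

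**What the plan says.** The expansion after the phase IIa part is meant to compare viral reduction between a low-match group (1/8 to 3/8) and a high-match group (4/8 to 8/8), on the hypothesis that low matching is not worse. Section 5.2 gives the sizing:

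- Design: "The sample size is calculated based on non-inferiority trial for comparing two-sample means".
- Variability: "Based on the preliminary data, the standard deviation of viral reduction is about 18". No unit is given.
- Margin: a difference (low minus high) of -10.
- Allocation: "the ratio of sample size between the low and high HLA matching groups is 5 to 7", which becomes 30 low-match and 42 high-match patients, 72 in total.
- Claim: this sample size "would have at least 85% power to test the non-inferiority hypothesis with 2-side 5% alpha level".
- Enrolment: "Assuming 10% of patients to be lost to follow-up, then the study will recruit up to a total of 80 patients".

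Section 5.4 names the two-sample t-test for the low versus high comparison. No true difference between the groups is stated as a planning value.

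**The concern.** Apart from the true difference, every input to the power calculation stands in one paragraph, so the figure can be checked directly. A margin of 10 against a standard deviation of 18 is a little over half a standard deviation. With 72 patients split 30 to 42, that looks too small for 85% power at a two-sided 5% level.

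The figure matters because it fixes the final sample size. The decision to expand depends on the phase IIa responses, but the number 80 comes from this calculation. Section 2.2 says it is unclear how much matching is needed for clinical activity, and this comparison addresses that question. If power is well below the stated figure, an inconclusive result is quite likely even when the groups do not differ. A reader who trusts 85% could then take it as evidence against low-match lines.

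**Working it through.** **Inputs.** From section 5.2: SD 18, margin 10, n = 30 (low) and 42 (high), two-sided 5%, which is one-sided 2.5% for non-inferiority. From section 5.4: two-sample t-test. Assumed: true difference 0.

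**Standard error of the difference**

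SE = 18 × √(1/30 + 1/42) = 18 × √0.05714 = 4.303

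Margin / SE = 10 / 4.303 = 2.324

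**Power at the stated alpha**

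Normal approximation: Φ(2.324 − 1.960) = Φ(0.364) = 64.2%

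Noncentral t with 30 + 42 − 2 = 70 degrees of freedom: 63.0%

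The plan says at least 85%, so the gap is 21 to 22 percentage points.

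**Dropout step.** 72 / (1 − 0.10) = 80. This part reproduces.

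**Other readings, true difference 0**

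| Reading | t | Normal |
|---|---|---|
| One-sided 2.5%, 30/42 (as stated) | 63.0% | 64.2% |
| One-sided 5%, 30/42 | 74.4% | 75.1% |
| One-sided 2.5%, equal split 36/36 | 64.2% | 65.4% |
| One-sided 2.5%, all 80 evaluable (33/47) | 67.6% | 68.7% |
| One-sided 10%, 30/42 | 84.8% | 85.1% |

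Only the last row comes close to 85%, and it contradicts the stated alpha. Leaving out the variance of the 42-patient group also gives a similar figure: Φ(10 / (18/√30) − 1.960) = 86.1%. That is not a two-sample calculation. The documents do not show how the 85% arose, and the conclusion does not depend on it.

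**Rounding of the SD** (t, one-sided 2.5%): SD 17 gives 68.0% and SD 19 gives 58.4%, so the word *about* in front of 18 does not explain the gap.

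**Sensitivity to the true difference**, low minus high (t, one-sided 2.5%, 30/42)

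| True difference | −2 | 0 | +1 | +2 | +3 |
|---|---|---|---|---|---|
| Power | 45.0% | 63.0% | 71.3% | 78.5% | 84.6% |

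**What would give 85% at one-sided 2.5%**, changing one input at a time

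- Margin: (1.960 + 1.036) × 4.303 = 12.9 (normal), or 13.1 (t), instead of 10.
- SD: 10 / (2.996 × 0.2390) = 14.0 (normal), or 13.8 (t), instead of 18.
- Sample size at 5:7: n(high) = 18² × (7/5 + 1) × 2.996² / 10² = 69.8, so 70 high and 50 low, 120 evaluable. With 10% loss, 120 / 0.9 = 133.3, so 134 recruited. By the t-test, 50/70 gives 84.5%, and 51/71 (122 evaluable) passes 85%.
- At one-sided 5%, the normal approximation gives 40 + 56 = 96 evaluable, still more than 72.

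**The case against.** The strongest objection is that power for non-inferiority depends on the true difference, and the plan gives none, so 63% follows from the plan's inputs plus an assumption. That is correct, and the figure should carry the condition. It does not rescue the claim. Zero is the conventional choice for a hypothesis that one group is not worse than the other. To reach 85%, low-match lines would have to be truly better by about 3 units, and nothing in the documents suggests such a planning value. If low matching were slightly worse, by 2 units and so well inside the margin, power would be 45%.

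A second objection concerns weight. This is a pilot study whose primary endpoints are feasibility and safety, and the effect of HLA matching is one of several secondary endpoints. The error does not touch the two-stage response design or the toxicity boundary. That stands. But the plan gives this comparison a formal hypothesis, margin, alpha and power, and derives maximum enrolment from them. The exploratory label in section 5.4 follows the longitudinal and correlation modelling and does not withdraw the power statement in section 5.2.

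A third objection is that the documents do not say what would follow from a failed comparison. Section 2.4.1.4 already ranks confirmed virus-specific activity through a shared allele above overall HLA match. That also stands. A misreading of a failed test is a risk created by the overstated power; the plan does not prescribe it.

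**Conclusion.** The stated power is wrong as written. With 30 and 42 evaluable patients, SD 18, margin 10, two-sided 5% and a true difference of 0, power is 63.0% by the planned t-test (64.2% by the normal approximation), against a stated minimum of 85%. The risk of failing to show non-inferiority when the groups are equal is about 37%, not at most 15%. Neither a one-sided 5% level, nor full evaluability of all 80 patients, nor rounding of the SD closes the gap, and no other part of the documents corrects the figure. The result rests on one assumption outside the documents, the true difference of 0. Because this figure fixes the final sample size, it must be corrected.

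**What to change.** Replace the power statement in section 5.2 in one of two ways:

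- With 72 evaluable patients (30/42), SD 18, margin 10 and a true difference of 0, power is about 63% at two-sided 5%; or
- The comparison has 85% power at two-sided 5% only for a margin of about 13. A wider margin would then need its own justification.

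In either case, state the assumed true difference and the unit of the SD and margin. If the 85% was calculated with a different SD, margin, alpha or assumed difference, give those values instead.

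It would also help to present the result mainly as an estimate with its 95% confidence interval. The expected half-width is 1.994 × 4.303 = 8.6, which shows directly what the data can exclude. This is optional and would need a matching line in section 5.4.

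The cost is one less favourable sentence in section 5.2. The cap of 80 stays and no extra patients are needed. Keeping the 85% claim at SD 18 and margin 10 would instead require about 120 evaluable patients, or about 134 recruited with 10% loss.
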